13.0 CRITERIA FOR REMOVAL FROM STUDY

a) A patient will come off study if the patient/parent administers an opioid or any analgesic within 24 (+4 hours) after the bone marrow procedure that is not in accordance to the algorithm provided to them.

b) If at any time the patient develops life-threatening grade 4 toxicity during the study period, he/she will be removed from study.

c) If a patient is found to be ineligible for two sequential bone marrow procedures as designated in Section 6, the patient will be removed from study.

d) The patient may withdraw from study at any time if the patient/parent desires.

14.0 BIOSTATISTICS

This is a randomized two arm cross-over study investigating the effectiveness of the addition of ropivacaine to the standard of care on pain among pediatric neuroblastoma patients undergoing repeated procedures. The two drug combinations are standard of care (Intervention A) or standard of care plus ropivacaine (Intervention B, see Section 4.1). Patients will be randomized to either Arm 1 (AB sequence) or Arm 2 (BA sequence, see Figure in Section 1) to determine whether standard of care or standard of care plus ropivacaine will be administered in the first of two procedures. Patients will cross over during the second procedure. Sample size calculation is based on the primary outcome: the proportion of patients requiring post-procedural opioid analgesia ("rescue opioids") within 24 hours (+/- 4 hours) post procedure. A needs assessment conducted in pediatric patients at MSKCC suggests that this proportion is about 30% under Intervention A (standard of care). We plan to enroll 50 patients (total of 100 procedures).

This is a crossover study in which we assume that there will be no period effect (i.e., if patient's response in the subsequent procedure is affected by the drug from the first procedure). Due to the estimated two month interval between the two procedures and the duration of action of less than 15 hours for either drug combinations, we can assume no period effect. The primary outcome (whether the patient received rescue opioids) will be evaluated with GEE (generalized estimating equations) for binary data with logit link function clustered by patients²³. The model

will include the drug indicator, procedure order, and an exchangeable correlation structure to address the correlation between multiple observations from the same patient. GEE has the advantage of being able to include data from only one of a patient's two procedures, in order to accommodate the (rare) case in which the patient drops out / withdraws prior to the second procedure. With complete data, however, this approach simplifies to a McNemar's test. The power and sample size calculations will be based on McNemar's test.

There is limited publication on the correlation among longitudinal measures of pediatric pain scores, particularly those reported by the parent instead of the child; one study reported correlation of 0.63 between times 1 and 2 (6 months apart) of parent-proxy reported pain scores²⁴. Assuming a conservative correlation of 0.4 between the two outcomes (from two procedures) of the same patient, a sample size of 45 patients will allow 80% power to detect an absolute difference of 20% in proportions between the treatments at an alpha level of 0.05 (assuming rates of 30% in Intervention A and 10% in Intervention B). This sample size allows for an interim assessment of futility at the half way point (23 out of 45 patients with both procedures completed). If $p > 0.703$, then the trial will stop for futility; if $p \leq 0.703$ then the study will continue until completion. The target enrollment of 50 patients allows for an anticipated drop-out rate (due to any reason) of 10% in the power analysis calculation. This power calculation was generated using the proc power procedure in SAS 9.4, specifying paired proportions and correlation for McNemar exact conditional test. Based on an accrual rate of 15 patients in month 1, 10 patients in months 2 and 3 and 5 patients per month in months 4, 5, and 6, we anticipate completion of enrollment in 6 months.

The potential variability between attending physicians performing the procedure will be explored by including specification of patients nested within physicians as clusters in the GEE models. Other potential factors to include in the GEE models as fixed effects may include total number of biopsies and aspirations per procedure and/or different dose of ropivacaine.

Secondary outcome of standardized cumulative opioid consumption within 24 hours (+/- 4 hours) (morphine equivalents, mg/kg/day) will be summarized and compared between the two drugs using linear GEE models with the same factors as described above, including of the other potential factors identified from the analysis of the primary outcome. Additionally, time to first opioid use within the first 24 hours (+/- 4 hours) post procedure will be estimated using the Kaplan-Meier method and compared between the two drugs using the clustered logrank test. This is appropriate as patients may never require any opioids and will hence be censored at 24-hours. The proportion of patients requiring non-opioid analgesia within 24 hours (+/- 4 hours) of procedure will be compared between the two drugs using GEE (for binary data) as described for the primary outcome.

Post-operative pain reported on the Wong-Baker FACES® Pain Rating Scale (converted to scale of 0-10) will be measured at 3 time points: in the PRR, at 6 hours (+/- 1 hour) and 24 hours (+/- 4 hours) after the procedure. If more than one pain score is recorded during the PRR,

then the maximum pain score during the PRR will be included in analyses. Pain scores will be compared between the two drugs using a linear GEE model with drug indicator, procedure order and the exchangeable correlation structure for the 3 time points. The GEE models appropriately account for correlation among within-individual repeated measures, sequence of drugs, and allow for missingness (i.e., if the respondent does not provide complete follow-up data). Short-term QOL and activity level will be reported based on the (NIH PROMIS® Parent Proxy Item Bank v1.0 – Pain Interference) as individual items. QOL measures will only be recorded once at 24-hours post-procedure. We will use a linear GEE model to analyze the differences in QOL item-measures between the two drugs. Drug indicator and procedure order will be included as covariates. Overall rate of any complications or major adverse events and the rates of specific adverse outcomes related to the addition of local ropivacaine will also be compared between drugs using GEE (for binary data). These analyses are exploratory because they are of secondary interest and we do not have prior data to estimate statistical power.

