2.1 OBJECTIVES AND SCIENTIFIC AIMS

Primary Objective:

- Determine whether there is a reduction in the percentage of pediatric neuroblastoma patients undergoing a bone marrow procedure who require post-procedural opioid analgesia within 24 hours (+/- 4 hours) of the procedure with the addition of local ropivacaine.

Secondary Objective:

Determine whether there is a difference in:

- 24 hours (+/- 4 hours) post-procedure opioid consumption in morphine equivalents (mg/kg/day)
- Percentage of patients requiring non-opioid analgesia within 24 hours (+/- 4 hours) of procedure
- Standardized pain scores (Wong-Baker FACES® Scale)
- Time to first opioid medication
- Short-term quality of life
- Adverse outcomes with the addition of local ropivacaine

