9.0 TREATMENT/INTERVENTION PLAN

Each enrolled patient will serve as his/her own control. On two bone marrow procedures, patients will receive either **intervention A** or **B**.

Each procedure will occur at approximately a two to four month interval. The timing of bone marrow procedures will be determined by the patient's clinical course.

In Intervention A, standard of care dosing and administration will be at the discretion of the anesthesiologist according to standard of care in the Department of Anesthesia at Memorial Sloan Kettering Cancer Center. In Intervention B, 2mg/kg of 0.5% ropivacaine will be drawn into

pre-filled syringes with a maximum dose of 20ml = 100mg. The physician performing bone marrow procedures will administer ropivacaine.

Ropivacaine will be injected into the subcutaneous tissue in an area approximately 1 cm in diameter. Subsequently, the ropivacaine will be administered to the periosteum in an area approximately 2-3 cm in diameter. Four pre-filled syringes will be provided and proceduralist physicians will be advised to administer one full syringe volume for each site (0.5mg/kg) with equal distribution between the subcutaneous and periosteal injection per site. Currently, propofol alone is the standard of care in the Department of Pediatrics at Memorial Sloan Kettering Cancer Center. While ropivacaine is a well described local anesthetic agent, the addition of ropivacaine to propofol to minimize post procedure pain is an experimental intervention.

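### The interim futility rule states no sidedness or direction for p; read two-sided, it stops near-null results but continues results that go against ropivacaine

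*Combined protocol and SAP*

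**What the plan says.** The primary objective in section 2.1 is directional: "Determine whether there is a reduction in the percentage of pediatric neuroblastoma patients" who need opioids after the procedure when ropivacaine is added.

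Section 14.0 places a futility look at 23 of 45 patients with both procedures done. The whole rule is "If $p > 0.703$, then the trial will stop for futility"; at or below that value, "then the study will continue until completion". No other section mentions the look.

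On the test, section 14.0 says the primary outcome "will be evaluated with GEE (generalized estimating equations) for binary data with logit link function clustered by patients", and adds that this reduces to McNemar's test when the data are complete. The power calculation was run "specifying paired proportions and correlation for McNemar exact conditional test". Alpha is 0.05, with no sidedness. No derivation is given for 0.703.

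**The concern.** A futility rule should stop a trial that is unlikely to meet its objective, so the chance of stopping should rise as the new treatment looks worse. A two-sided p cannot do that alone: it is large near no difference and small for a strong result in either direction. If p is two-sided, the rule halts trials that look neutral and sends on trials in which ropivacaine looks harmful. If p is one-sided for benefit, strongly adverse results stop.

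The two readings give opposite decisions on the same adverse data, and the text does not choose between them. Unless it is settled beforehand, the reading will be chosen with the data in hand. On the two-sided reading, the remaining 45 − 23 = 22 pairs would be completed after an adverse interim result, some of them with little prospect of showing the reduction that the trial seeks.

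**Working it through.** **Inputs from section 14.0:** rates 30% (A) and 10% (B), within-patient correlation 0.4, 45 pairs, alpha 0.05, look at 23 pairs, cut 0.703.

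**Assumptions:** the rates 30/30, 30/40 and 30/50 are illustrative, each with correlation 0.4. Asymptotic McNemar is uncorrected. The final test is two-sided at 0.05.

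Write b for patients with opioid use under A only and c for those under B only; results are given as b vs c.

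**1. The plan's own figure.** P(both) = 0.3×0.1 + 0.4×√(0.3×0.7×0.1×0.9) = 0.030 + 0.055 = 0.085. So A-only = 0.30 − 0.085 = 0.215 and B-only = 0.10 − 0.085 = 0.015. Summing the probabilities of all (b, c) that reach significance by exact McNemar gives:
- two-sided 0.05: 79.6% at 44 pairs and 80.9% at 45, so the stated 45 is reproduced;
- one-sided 0.025: also 80.9% at 45;
- one-sided 0.05: 88.3% at 45.

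The sizing therefore fits a two-sided 0.05 test, but this does not fix the sidedness of the interim p.

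**2. What 0.703 means.** Two-sided, p > 0.703 is |z| < 0.38, a band around no difference. One-sided for benefit, it is z < −0.53.

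**3. Decisions on particular results.** With X ~ Bin(b+c, ½), exact two-sided p = min(1, 2·P(X ≤ min(b,c))) and exact one-sided p = P(X ≥ b). Asymptotic z = (b−c)/√(b+c). For 3 vs 2, z = 1/√5 = 0.447. For 0 vs 5, exact p = 2×(½)⁵ = 0.0625.

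| b vs c | Exact two-sided | Asymptotic two-sided | Exact one-sided |
|---|---|---|---|
| 3 vs 2 | 1.00, stop | 0.655, continue | 0.500, continue |
| 4 vs 4 | 1.00, stop | 1.00, stop | 0.637, continue |
| 0 vs 5 | 0.0625, continue | 0.025, continue | 1.00, stop |
| 1 vs 8 | 0.039, continue | 0.020, continue | 0.998, stop |

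**4. Chance of stopping at 23 pairs**, by enumeration with the cell probabilities for each pair of rates:

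| A/B rates | Exact two-sided | Asymptotic two-sided | Exact one-sided | Continues with B numerically worse, two-sided (exact / asymptotic) |
|---|---|---|---|---|
| 30/10 | 6.1% | 1.5% | 1.3% | 0.05% / 0.35% |
| 30/30 | 52.9% | 28.3% | 43.6% | 23.5% / 35.8% |
| 30/40 | 37.2% | 19.9% | 77.5% | 57.7% / 70.3% |
| 30/50 | 12.9% | 6.1% | 95.3% | 86.5% / 92.5% |

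From 30/30 downwards, two-sided stopping falls as ropivacaine gets worse; one-sided stopping rises.

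**5. How adverse the continuing results are.** At 30/30, 16.4 of the 23.5 points (exact) are a net excess of two or three patients, and 9.4 of the 35.8 points (asymptotic) are a net excess of one. Results at least as adverse as 0 vs 5 (exact p ≤ 0.0625 against B) occur in 1.2% of trials at 30/30 and 8.2% at 30/40.

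**6. Prospects after continuing**, if all later pairs follow 30/10, with 22 pairs left (or 50 − 23 = 27 if all 50 enrolled patients complete):
- After 0 vs 5, the chance of ending in significant benefit is 0.0003% / 0.009% (exact) or 0.002% / 0.042% (asymptotic).
- After 0 vs 2, it is 0.84% / 3.6% (exact) or 2.5% / 8.1% (asymptotic).
- After 0 vs 1, which continues only with the asymptotic test, it is 14.0% / 27.5%.

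**7. Power and error including a two-sided look.** At 30/10 with an exact look and exact final test, power is 79.4%, with or without a condition that also stops when B is no better than A. With asymptotic tests at both it is 88.3% either way. A one-sided exact look with an exact final test gives 80.7%. False claims of benefit at 30/30 are 1.1% (exact) or 2.1% (asymptotic), with or without the condition.

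**The case against.** **The test is not wholly unnamed.** A reader might infer that no test can be identified for the look. Section 14.0 does not support that: it says GEE reduces to McNemar with complete data, and the look uses patients with both procedures done. This stands. What stays open is exact or asymptotic, and that choice changes decisions (3 vs 2).

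**The adverse cases are mostly mild.** A reader might infer that clearly harmful results would often be carried on. The counts in step 5 do not support that, and the rates of 40% and 50% under ropivacaine have no basis in the documents. This also stands, and it limits the size of the concern.

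**One-sided may have been meant, or two-sided may be deliberate.** Either is possible. A two-sided plan that runs on could formally show worsening: at the assumed 30/40 the chance is 15.6% (exact) or 22.2% (asymptotic) under the two-sided rule, and under 0.1% with a direction condition. Completing the trial also yields more data on "Overall rate of any complications or major adverse events and the rates of specific adverse outcomes related to the addition of local ropivacaine". These are legitimate reasons, but the plan states none of them and the primary objective is a reduction.

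**Other monitoring exists.** Sections 16.2 and 13.0 cover institutional safety monitoring and removal of a patient for grade 4 toxicity. Neither gives the look an efficacy direction.

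**Conclusion.** The concern holds in a limited form. The rule omits sidedness, direction, the version of McNemar and the basis of 0.703. On the two-sided reading, which the sizing favours without proving, stopping becomes less likely as ropivacaine gets worse (52.9%, 37.2% and 12.9% with the exact test at 30/30, 30/40 and 30/50).

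Its practical reach is modest. The problem matters only if ropivacaine does not help. Most adverse results that continue are small, and after marginal ones a significant benefit is still possible, so no general claim of hopelessness is made. For results like 0 vs 5 the chance of ending in benefit is below 0.1%.

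A reader might also infer inflated false-positive error or a serious loss of power. The figures show neither: the exact two-sided look takes power from 80.9% to 79.4%. The figures rest on correlation 0.4, 23 pairs at the look and, for step 7, 22 pairs after it. The rule should be completed before the look takes place, because two competent statisticians could apply it and reach opposite decisions.

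**What to change.** In section 14.0:

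- Name the interim test (exact or asymptotic McNemar) and state whether p is one- or two-sided.
- State how 0.703 was derived and confirm that it belongs to the test and sidedness chosen. The documents do not allow this to be checked, so the cut should not simply be carried over.
- Add a direction, in one of two ways. (a) Keep a two-sided p and also stop when the observed opioid rate under B equals or exceeds that under A. (b) Define p as one-sided for benefit. Under (b) with the exact test some ties continue (2 vs 2, p = 0.688; 3 vs 3, 0.656; 4 vs 4, 0.637). With the asymptotic test, 11.6% of trials at 30/30 would still continue with ropivacaine numerically worse.
- Quote power including the look. With an exact look and exact final test it is 79.4% under (a) and 80.7% under (b).

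If GEE is preferred for the look, say so, and say what happens when no patient has opioid use under B. At 10% that has probability 0.9²³ = 8.9%, and the logit model then has no finite drug estimate.

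The cost is a few sentences and no extra patients. Adding the condition in (a) to a two-sided McNemar look leaves power at 30/10 unchanged to within 0.1 point. The sponsor should state the downside: stopping on an adverse trend gives up formally showing that ropivacaine is worse, and shortens the secondary and adverse-outcome data.

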10.0 EVALUATION DURING TREATMENT/INTERVENTION

Pain will be assessed in the post-anesthesia care unit (PRR). Directly upon emergence from anesthesia after the procedure and every 15 minutes subsequently, PRR nurses will use the Wong-Baker FACES® Pain Rating Scale (Appendix 1). Nurses will record patient-reported pain scores and administered analgesia in the Electronic Medical Record (EMR). Analgesia doses will be recorded at the time of administration. The PRR nurses will follow a standardized post-procedural algorithm (Appendix 2.1). Patients will recover in the PRR for approximately 30 to 90 minutes prior to discharge from MSKCC. In some instances, patients will be discharged from the PRR to the Neuroblastoma Clinic in the Pediatric Day Hospital (PDH). We anticipate that all patients will be discharged from MSKCC before 6 hours from the end of their procedure. In the unexpected case that a patient is admitted to the hospital for any reason during the study period (28 hours post-procedure), study investigators will provide the inpatient RN with the post-procedural opioid management algorithm (Appendix 2.1). Only if the admission is due to a study related life-threatening grade 4 toxicity, will the admitted patient be removed from the study as described in Section 13.0.

Families will be provided a 2 part, 12 item written questionnaire with 4 items and 8 items in each part, respectively (Appendix 3). They will be asked to complete Part 1 at 6 hours (+/- 1 hour) and Part 2 at 24 hours (+/- 4 hours) following the procedure. This questionnaire will have items regarding pain intensity and management to be answered at both time points. Families will be asked to follow a post-procedure pain management plan (Appendix 2.2). Post-procedural quality of life (QOL) will be assessed using a four-item questionnaire (Appendix 3) adapted from the NIH PROMIS® Parent Proxy Item Bank for Pain Interference and approved for use by the MSKCC Behavioral Research Methods Core Facility. These four questions will include the domains of physical recovery, emotional and social functioning. QOL will be assessed about 24 hours (+/- 4 hours) following the procedure. Principal Investigators, Co-Investigators, Investigators or appropriate clinic staff will call families 24-72 hours following procedure to obtain answers to the questionnaire.

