12.0 CRITERIA FOR THERAPEUTIC RESPONSE/OUTCOME ASSESSMENT

12.1 To assess primary objective, we will determine and compare for each study intervention the percentage of patients who required opioid analgesia between the time of bone marrow procedure and 24 hours (+/- 4 hours) after the procedure.

12.2 For the secondary objectives:

- a) We will determine and compare for each study intervention the percentage of patients who used any non-opioid analgesia within 24 hours (+/- 4 hours) after bone marrow procedure.
- b) We will calculate and compare for each study intervention the total dose of opioid consumption within 24 hours (+/- 4 hours) of the bone marrow procedure using mg/kg/day morphine equivalent.

Drug	IV conversion factor	PO conversion factor
Morphine	10mg	30mg
Fentanyl	0.250mg (250mcg)	—
Hydromorphone	2mg	8mg
Oxycodone	—	20mg
Oxymorphone	1mg	10mg
Codeine	75mg	130mg
Methadone	1mg	2mg
Hydrocodone	—	30mg

c) We will also determine the time to the first opioid administration. The starting point for this time will be the time of transfer to the PRR which will be documented by the PRR RN. This time will be recorded on the parent worksheet by the PRR RN.

d) We will assess standardized pain scores at 3 time points: (1) the maximum recorded pain score in the PRR, (2) at 6 hours (+/- 1 hour) and (3) 24 hours (+/- 4 hours) after the bone marrow procedure. Pain scores 2 and 3 will be recorded by the parent after discharge from MSKCC. We will use the following validated pain scales: Wong-Baker FACES® Pain Rating Scale for patients between 3-18 years of age for patient-reported pain when asked by post-anesthesia recovery room nurses upon emergence from anesthesia and by inpatient nurses or family members in the outpatient setting upon discharge from the post-anesthesia recovery unit. We will compare pain scores between study interventions.

e) The QOL metric is a brief instrument that will assess post-procedural quality of life within 24 hours (+/- 4 hours) of the bone marrow procedure. This instrument assesses the following domains: sleep, physical functioning, emotional functioning and social functioning. This brief measurement tool will be adapted from a validated metric for pain interference in pediatric patients: NIH PROMIS® Parent Proxy Item Bank v1.0 – Pain Interference, which is a 13-item questionnaire. However, given that our study has rapid, frequent assessments, we will use an

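### Opioid endpoints use a 24 (+/- 4) h window but time to first opioid is censored at a fixed 24 h, so late events and early-closed records are handled inconsistently

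*Combined protocol and SAP*

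**What the plan says.** The tolerance is part of the outcome definitions. The primary objective (section 2.1) concerns patients "who require post-procedural opioid analgesia within 24 hours (+/- 4 hours) of the procedure", and section 12.1 counts those who "required opioid analgesia between the time of bone marrow procedure and 24 hours (+/- 4 hours) after the procedure". Section 12.2(b) measures "total dose of opioid consumption within 24 hours (+/- 4 hours) of the bone marrow procedure using mg/kg/day morphine equivalent". Section 14.0 repeats the window for consumption and for non-opioid analgesia, and it analyses "time to first opioid use within the first 24 hours (+/- 4 hours) post procedure" by Kaplan-Meier and a clustered logrank test. The next sentence of section 14.0 reads: "This is appropriate as patients may never require any opioids and will hence be censored at 24-hours".

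The same tolerance governs home reporting: section 10.0 asks families to complete "Part 2 at 24 hours (+/- 4 hours) following the procedure". A call follows at 24 to 72 h, and section 12.2(e) limits it to collecting answers already recorded.

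Time zero also differs. Section 12.1 counts from the procedure, whereas for time to first opioid section 12.2(c) says "The starting point for this time will be the time of transfer to the PRR".

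Three other windows appear. Section 10.0 gives a study period of 28 h. Section 13.0(a) gives a removal window of 24 h plus 4 h with no minus side. The needs assessment in section 3.2, which supplies the planning rate of about 30%, used a plain 24 h.

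**The concern.** A tolerance of 4 h either side suits the timing of a questionnaire. As part of an endpoint definition, it leaves the end of observation open. Three things follow.

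- The primary and time-to-event analyses can disagree about the same child. A first opioid between 24 and 28 h counts in one and lies beyond the censoring time of the other.
- A patient whose dose record ends at 20 h is treated as known to be opioid-free to 24 h.
- Each child is his or her own control, yet nothing keeps the two observation periods equal.

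The consumption unit adds a smaller ambiguity. The total is cumulative over 20 to 28 h but is expressed per day, and the plan does not say whether it is rescaled. Left open, these choices fall to the analyst after the data are in.

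**Working it through.** **1. The plan's own figure.** Inputs from section 14.0: 30% versus 10%, correlation 0.4, alpha 0.05, exact conditional McNemar test, 45 patients.

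- Both-positive cell: 0.30 × 0.10 + 0.4 × √(0.30 × 0.70 × 0.10 × 0.90) = 0.0850.
- Discordant cells: 0.30 − 0.0850 = 0.2150 and 0.10 − 0.0850 = 0.0150.
- Two-sided exact power at 45 is 80.9%, and 45 is the smallest number that reaches 80%. The plan does not state sidedness; two-sided reproduces it.
- 45 / 0.90 = 50, as stated.

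These rates are not tied to a floating window, so fixing the window at 24 h leaves the calculation unchanged.

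**2. Window length.** 24 − 4 = 20 h and 24 + 4 = 28 h. The spread is 8 h, and the ratio is 28/20 = 1.4.

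**3. The censoring rule applied literally.** Hypothetical counts: 50 procedures under standard of care with 30% use, so 15 first opioids, of which 14 occur before 24 h and one at 26 h. The small gap between procedure and PRR transfer is ignored.

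- Primary endpoint: 15/50 = 30%.
- Kaplan-Meier at 24 h: 1 − 36/50 = 28% use.
- The 35 event-free procedures are then censored at 24 h, so the risk set at 26 h is the one late case. The survival estimate is 36/50 × (1 − 1/1) = 0, which means estimated use of 100%.
- In an ordinary logrank test, if that is the only procedure still at risk under either intervention, observed and expected are both 1. The late event adds nothing to the comparison.

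One late opioid therefore takes the curve to 100% use and has no weight in the test.

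**4. Sensitivity of the binary endpoint.** The documents give no distribution of opioid times. Assume a constant hazard that gives the planned rates at 24 h, so use by time T is 1 − (1 − p)^(T/24).

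| Window closes at | A (p = 0.30) | B (p = 0.10) | Difference | Power at 45 |
|---|---|---|---|---|
| 20 h | 25.7% | 8.4% | 17.3 | 70.8% |
| 24 h | 30.0% | 10.0% | 20.0 | 80.9% |
| 28 h | 34.0% | 11.6% | 22.5 (unrounded rates) | 87.6% |

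Each row assumes that every procedure closes at that hour, so the 20 h and 28 h rows are extremes.

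**5. Expected effect.** Keep the constant hazard and let closing times be uniform over 20 to 28 h under both interventions. Mean use is 1 − [24 / (8 × −ln(1 − p))] × [(1 − p)^(20/24) − (1 − p)^(28/24)].

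- A: 1 − (3/0.3567) × (0.7429 − 0.6596) = 29.96%.
- B: 1 − (3/0.1054) × (0.9159 − 0.8843) = 10.00%.
- Difference: 19.96 points, a loss of about 0.04.

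If every first opioid falls before 20 h, window length does not affect the binary endpoint at all.

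**6. Consumption.** Rescaling a given total to 24 h multiplies it by 24/20 = 1.20 or 24/28 = 0.86. The plan does not say whether this is done.

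**The case against.** The strongest reply is that 24 hours in the censoring sentence is a nominal label. Section 14.0 also describes quality of life as recorded at 24 hours, although sections 10.0 and 12.2(e) give the same assessment a 4 h tolerance, and the censoring sentence directly follows one that states the tolerance. This is a fair reading of intent, but it does not supply a rule. A nominal 24 h still does not say where a 20 h or a 28 h record is censored.

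Second, the questionnaire and parent worksheet are not available here. If they hold dose times, doses after 24 h can be cut off at analysis. That an early Part 2 closes dose recording is an inference. However, no section says that recording continues to a common hour.

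Third, PRR transfer is a legitimate, documented start for time to first rescue, and the word standardized may imply that consumption is rescaled. Both stand: these are matters of ambiguity or preference, not errors.

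A reader might infer from the table in the working that the window moves the primary result by about 8 points (34.0 − 25.7 = 8.3 under A). The documents do not support that. It compares every A procedure closed at 20 h with every A procedure closed at 28 h. Section 4.2 blinds patients, parents, recovery nurses and post-procedural data collectors, so there is no evident route by which closing time would track intervention.

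**Conclusion.** The plan should be changed on this point. The defect is one of definition: a stated censoring rule does not fit a stated endpoint window, and followed literally it gives an unusable Kaplan-Meier tail and unobserved event-free time. The time-to-event analysis is the most exposed. It is one of the secondary analyses that section 14.0 calls exploratory.

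For the primary endpoint the expected effect is small: about 0.04 points under a constant hazard with closing times uniform over 20 to 28 h and unrelated to intervention. The real figure depends on the share of opioid use that is late, which the documents do not give. The expected harm is noise in the within-child comparison and inconsistency between endpoints.

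It would go too far to conclude that the trial is biased toward either intervention or that it is underpowered. Blinding and randomised sequence argue against the first. The planned 80% at 45 reproduces and is unaffected by the fix.

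**What to change.** 1. Define all opioid and non-opioid endpoints on one fixed analysis window, for example 0 to 24 h, the length used in the needs assessment.
2. Count it from one time zero that is actually documented. PRR transfer is recorded (section 12.2(c)); the end of the procedure is not stated to be. If PRR transfer is chosen, state how opioids given during the procedure are treated, because section 12.1 counts from the procedure.
3. Keep the 4 h tolerance only for completing Part 2.
4. Censor time to first opioid at the end of the window or at the last time dose status is known, whichever is earlier.
5. Report consumption as mg/kg over the fixed window.
6. Amend section 12.2(e) so that the existing 24 to 72 h call, made after the window has closed, may collect doses given between an early Part 2 and the end of the window.
7. Reconcile the 28 h study period in section 10.0 and the removal window in section 13.0(a) with the endpoint window.

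The cost is protocol wording and a small change to the call script, with no added visits or patients. The downside is that doses after the cut-off are listed but not counted.
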